### 2.1 Investigational Sites

The study will be conducted in approximately 50 sites in North America, Europe, Middle East, South America, and Asia Pacific, including approximately 10 sites in the USA.

### 2.2 Study Coordination / Monitoring

The Sponsor will coordinate the study and will utilize the support of 1 or more CROs for some activities of the study. The Sponsor will perform oversight of the activities performed by the CROs.

The Clinical Study Supplies department of the Sponsor will supply the study medication of avelumab. Clinical supply is performed by the Clinical Trial Supply function of the Sponsor.

Subject enrollment will be managed by an interactive response technology (IRT) system. Safety laboratory assessments will be performed locally. Results from these local laboratories will be recorded according to the electronic case report form (eCRF) completion guidelines.

Pharmacokinetic (PK), CCI [REDACTED], immunogenicity, and CCI [REDACTED] will be performed centrally under the responsibility and/or supervision of the Sponsor.

The Global Drug Safety Department, Merck KGaA, Darmstadt, Germany, or their designated representatives will supervise drug safety and the timely reporting of adverse events (AEs) and serious adverse events (SAEs).

Quality assurance of the study conduct will be performed by the Development Quality Assurance Department, Merck KGaA, Darmstadt, Germany.

The Department of Global Biostatistics will supervise the statistical analyses, which will be outsourced to QuintilesIMS.

## 2.3 Safety Monitoring Committee

A Safety Monitoring Committee (SMC) will review the safety and available PK data on a regular basis. The SMC will consist of permanent members from the Sponsor (Global Drug Safety Product Leader, Medical Responsible, Clinical Pharmacologist, and Biostatistician) and/or CRO (Early Clinical Development Lead, Medical Lead, Biostatistician, and Global Drug Safety Representative), the participating Investigator(s) (for Phase I-recommended Phase II dose [RP2D] portion only), and other optional members with expertise in the management of pediatric cancer subjects. Ad hoc members may be invited as needed. More details will be described in the SMC Charter.

The SMC will decide on relevant dose-limiting toxicities (DLTs) for protocol criteria and will decide by consensus on dose escalation, dose de-escalation, suspension of enrollment, and/or declaration of the maximum tolerated dose (MTD) and/or RP2D, with the final adjudication being a Sponsor prerogative. In addition, the SMC may decide to study a specific cohort.

The SMC may modify the frequency of meetings as deemed appropriate by the SMC during the course of the trial. The specific working procedures will be described in an SMC Charter, which will be established prior to the start of recruitment.

## 3 Background Information

### 3.1 Programmed Cell Death and Ligands

The programmed death 1 (PD-1) receptor and PD-1 ligands 1 and 2 (PD-L1, PD-L2) play integral roles in immune regulation. Expressed on activated T cells, PD-1 is activated by PD-L1 and PD-L2 expressed by stromal cells, tumor cells, or both, initiating T-cell death and localized immune suppression (Dong 1999; Freeman 2000; Dong 2002; Topalian 2012a) and potentially providing an immune-tolerant environment for tumor development and growth. Conversely, inhibition of this interaction can enhance local T-cell responses and mediate antitumor activity in nonclinical animal models (Dong 2002; Iwai 2002). The PD-L1 molecule is expressed as an immune-inhibitory checkpoint on epithelial and vascular endothelial cells, as well as by a number of immune cells, and is employed by tumor cells as immune escape mechanism.

Agents targeting PD-L1, PD-1, and related molecules are collectively referred to as immune checkpoint inhibitors (ICIs). Clinical activity of ICIs, including avelumab, has been observed in

melanoma, non-small cell lung cancer (NSCLC), urothelial cell carcinoma, renal cell carcinoma, ovarian cancer, Merkel cell carcinoma (MCC), and Hodgkin's lymphoma, among others.

In the clinical setting, treatment with antibodies that block the PD-1 – PD-L1 interaction have been reported to produce objective response rates (ORRs) of 7% to 38% in subjects with advanced or metastatic solid tumors, with tolerable safety profiles (Brahmer 2012; Topalian 2012b; Hamid 2013). Notably, responses appeared prolonged, with durations of 1 year or more for the majority of subjects.

Several studies with checkpoint inhibitors in pediatric patients with cancer are currently ongoing. In a pediatric study of ipilimumab, no unexpected safety findings were noted, and early signs of clinical activity were seen in pediatric patients with cancer (Merchant 2016). A Phase II study of nivolumab showed no objective responses in patients with relapsed/refractory osteosarcoma, Ewing sarcoma, and rhabdomyosarcoma; Phase I data in relapsed/refractory solid tumors was not reported (Davis 2017). A Phase I/II study of pembrolizumab in pediatric patients with advanced melanoma or PD-L1+ advanced, relapsed, or refractory solid tumors or lymphomas showed low toxicity and durable antitumor activity in various tumor types, specifically Hodgkin's lymphoma, mesothelioma, malignant ganglioglioma, lymphoepithelial carcinoma, and adrenocortical carcinoma (Georger 2017a). The iMATRIX-Atezolizumab study examined atezolizumab in pediatric and young adult patients with refractory/relapsed solid tumors (Georger 2017b). Preliminary anti-tumor activity was seen in Hodgkin's lymphoma and in single patients with Ewing sarcoma and atypical malignant rhabdoid tumor. The pharmacokinetic and safety profiles for all drugs were similar in children as in adults. PD-L1 expression was variable across pediatric solid tumors subtypes.

### 3.2 Avelumab

The Investigational Medicinal Product (IMP) for this trial is avelumab, the International Nonproprietary Name for the Sponsor's anti-PD-L1 monoclonal antibody MSB0010718C. Avelumab is being developed in oncological settings by Merck KGaA, Darmstadt, Germany, and by its subsidiary, EMD Serono Research & Development Institute, Inc., Billerica, MA, USA.

Avelumab is a fully human immunoglobulin G1 (IgG1) monoclonal antibody that selectively binds to PD-L1 and competitively blocks its interaction with PD-1. Compared with anti-PD-1 antibodies that target T-cells, avelumab targets tumor cells. Therefore, it is hypothesized to have fewer side effects, including a lower risk of autoimmune-related safety issues, as blockade of PD-L1 leaves the PD-L2/PD-1 pathway intact to promote peripheral self-tolerance (Latchman 2001). For complete details of the in vitro and nonclinical studies, refer to the current Investigator's Brochure (IB).

Avelumab is currently under evaluation in several Phase I, II, and III studies in various tumor indications in the adult subject population, including NSCLC, gastric cancer, MCC, renal cell carcinoma, urothelial cancer, and ovarian cancer. In March 2017, the US Food and Drug Administration granted accelerated approval to avelumab for the treatment of patients 12 years of age and older with metastatic MCC. In May 2017, the indication was extended via accelerated approval to include patients with locally advanced or metastatic urothelial carcinoma, who have

disease progression during or following platinum-containing chemotherapy or within 12 months of neoadjuvant or adjuvant treatment with platinum-containing chemotherapy (Bavencio 2017).

More than 3,720 subjects have been treated with avelumab to date. In the dose-escalation portion of the Phase I study, there was no evidence of differences in the safety profile across all administered dose levels from 1 mg/kg to 20 mg/kg. The MTD was not reached.

The recommended Phase II/III dose in adults was determined to be 10 mg/kg avelumab administered intravenously every 2 weeks. Avelumab treatment is continued until confirmed progression, death, unacceptable toxicity, or any criterion for withdrawal occurs. Promising clinical activity was observed in several tumor types in adults. Refer to the most recent version of the IB for updated information regarding current clinical studies with avelumab.

### 3.3 Rationale for the Current Clinical Trial and Overall Benefit and Risk Considerations

This clinical trial will be conducted in compliance with the clinical trial protocol, ICH GCP, and any additional applicable regulatory requirements.

Based on the available nonclinical and clinical data to date (including modeling and simulation results using adult PK data from ongoing avelumab studies), the conduct of the trial specified in this protocol is considered justifiable.

Refer to the IB for further information about the nonclinical and clinical programs and guidance for the Investigator.

#### Rationale for the Current Clinical Trial

Based on the success of checkpoint inhibitor therapies in adult tumors, there is a rationale to explore their activity in pediatric malignancies. Pediatric tumors appear to bear the same hallmarks of sensitivity to ICIs, namely the presence of immune cell infiltrates, expression of PD-L1 in tumor and/or infiltrating immune cells (Geoerger, 2017a; Geoerger, 2017b) and high mutation burden in some cases (Marabelle 2015). The pediatric patient population in the Phase I part of this study will include subjects with common pediatric tumors, such as neuroblastoma and sarcomas, as well as rarer tumors occurring in subjects during childhood. Most pediatric tumors share several characteristics: they are predominantly of embryonal origin, have peak incidence in childhood and adolescence, and have well-established guidelines for their diagnosis and management in the first- and second-line settings. In contrast, tumors occurring in adults are generally carcinomas, which are extremely rare in children. These tumors are mostly of epithelial origin, and their incidence rises with age, usually starting in the third decade of life. Diagnosis and management of these tumors are usually extrapolated from adult data. Treatment of these tumors with ICIs have been studied extensively in adults, but very little data are available in children (Davis 2017; Geoerger, 2017a; Geoerger, 2017b).

Based on the acceptable safety and encouraging efficacy data of avelumab in adults, and the preclinical rationale supporting the role of the immune system in the pathogenesis of pediatric malignancies (Marabelle 2015), avelumab will be evaluated in a broad population of pediatric

patients with tumors. At the present time, there is no validated patient selection strategy in pediatric cancers. In the Phase I part of the study, the aims are to define the RP2D and assess the safety and tolerability of avelumab. The Phase II part of the study is designed to enable a formal statistical assessment and characterization of the antitumor activity of avelumab as determined by the ORR, and a robust statistical design to allow for clear conclusions to be drawn regarding the benefit of treatment with avelumab in pediatric patients with specified tumor types.

### Overall Benefit and Risk Considerations

The risk-benefit relationship has been carefully considered in the planning of the trial. Based on the available nonclinical and clinical information to date, avelumab provides a positive benefit-risk status with solid tumors, and the conduct of the trial is considered justifiable using the dose and dose regimen of avelumab as specified in this clinical trial protocol.

Specific risks associated with the use of avelumab as a monoclonal antibody have been observed. The primary risks of exposure to avelumab include infusion-related reactions (IRRs) and immune-related AEs (irAEs). Premedication with an antihistamine (H1 receptor blocker such as diphenhydramine) and with acetaminophen (paracetamol) approximately 30 to 60 minutes prior to each dose, once every 2 weeks for the first 4 infusions is mandatory. This regimen may be modified based on local treatment standards and guidelines, as appropriate.

## 4 Trial Objectives

### 4.1 Primary Objectives

#### Phase I

- To evaluate the safety and tolerability of avelumab
- To determine the RP2D of avelumab in pediatric subjects 0 to < 18 years of age with solid tumors and lymphoma

#### Phase II

- To assess antitumor activity of avelumab by determining the ORR according to RECIST 1.1 and as adjudicated by the Investigator in 2 expansion cohorts in specified tumor types in pediatric subjects treated with avelumab

### 4.2 Secondary Objectives

#### Phase I

- To assess antitumor activity of avelumab by determining the ORR according to RECIST 1.1 and as adjudicated by the Investigator in pediatric subjects with solid tumors and lymphoma treated with avelumab
- To assess progression-free survival (PFS) based on Investigator assessments, duration of response (DOR), time to respond (TTR), and overall survival (OS)
- To characterize the PK of avelumab
- To assess the immunogenicity of avelumab

- To evaluate PD-L1 expression; tumor-infiltrating T-cell activity; T-cell population; and T-cell, B-cell, and NK-cell numbers in tumor tissue at Baseline and at confirmed progression (if tumor tissue is obtained)
- To measure changes in vaccination-related antibody concentrations (diphtheria, tetanus, and pneumococcal conjugate)

CCI

## 5 Investigational Plan

### 5.1 Overall Trial Design and Plan

This is a multicenter, open-label, international, Phase I/II study to evaluate the dose, safety and tolerability, antitumor activity, PK, and pharmacodynamics of avelumab in pediatric subjects 0 to < 18 years of age with refractory or relapsed malignant solid tumors (including central nervous system tumors) and lymphoma for which no standard therapy is available or for which the subject is not eligible for the existing therapy.

The study will consist of 2 parts: the dose-finding part (Phase I) and the tumor-specified expansion part (Phase II). During Phase I, the RP2D of avelumab in children will be determined. During Phase II, 2 expansion cohorts will be enrolled, with specific tumors chosen based on available data from the Phase I part of the study, ongoing studies with avelumab and other ICIs, clinical and nonclinical chemotherapy combination data, and any published literature.

[figure not shown]
### 5.1.1 Overall Design

Planned number of subjects:

- Phase I: 12 to 36 subjects
- Phase II: 46 to 112 subjects (23 to 56 subjects per tumor type) for 2 cohorts

The trial design schematic is presented in Figure 1.

Figure 1 Schematic of the Trial Design

RP2D: recommended Phase II dose; TBD: to be determined.

#### 5.1.1.1 Phase I Study Design

In the dose-finding part of the study, subjects will be enrolled in sequential cohorts of 3 to 6 subjects each; the first 3 subjects will be  $\geq 1$  year old. At least 12 subjects must be evaluable for the primary analysis. Phase I will be completed when at least 12 DLT-evaluable subjects have been treated at a dose level confirmed to be safe. Phase II will then begin.

The starting dose will be the same as recommended dose in adults, 10 mg/kg avelumab administered intravenously (iv) once every 2 weeks, which is based on modeling and simulation results using adult PK data from ongoing avelumab studies as described in Section 5.2. Avelumab will be administered until confirmed progression, death, unacceptable toxicity, or any criterion for withdrawal occurs. In Phase I, the DLT observation period is defined as a 28-day period (2 cycles) beginning with the first avelumab administration.

The first cohort of 3 to 6 subjects will be enrolled at the starting dose level of 10 mg/kg (DL1). Based on the number of subjects experiencing DLTs at the completion of the first cohort, the dose for the next cohort of subjects can be kept the same or modified.

- If DL1 is confirmed as safe, this dose will be selected as RP2D if it provides adequate exposure in children compared with adults.
- If exposure is not adequate (when compared with adult population PK [PopPK]-simulated values for median and distribution of exposure [ $C_{max}$ , AUC, and  $C_{trough}$ ]), a decision can be made to escalate to a dose level up to 20 mg/kg (DL2).
- If at any point the modified toxicity probability interval (mTPI) results indicate a dose de-escalation is warranted, the next subjects will be enrolled at lower dose level of 3 mg/kg every 2 weeks (DL -1). Dose re-escalation can be permitted based on the mTPI results as long as the current dose level has not been determined to have exceeded the MTD. The MTD estimate is the highest dose tested of avelumab associated with the occurrence of DLTs within the first 2 cycles of treatment in < 33% of subjects, provided that a higher dose level of avelumab was tested and had an associated DLT rate  $\geq$  33%.

Subjects will return to the clinic at regular intervals for assessments (see Section 7.1 and Table 1).

Avelumab treatment will continue until:

- PD (see Section 5.5.1) or death
- Unacceptable toxicity
- Any criterion for withdrawal from the trial or trial treatment is fulfilled (see Section 5.5).

Treatment can continue past the initial determination of confirmed disease progression (see Section 6.2).

Subjects who have experienced a complete response (CR) should be treated for a minimum of 12 months based on clinical judgment of benefit and/or until confirmed progression per irRECIST (Bohnsack 2014), unacceptable toxicity, or any criterion for withdrawal occurs, after confirmation of response as specified in this protocol. In case a subject with a confirmed CR relapses after stopping treatment, during long-term follow-up but prior to the End of Trial, 1 re-initiation of treatment will be allowed at the discretion of the Investigator and agreement of the Medical Monitor. In order to be eligible for retreatment, the subject must not have experienced any toxicity that led to treatment discontinuation of the initial avelumab therapy. Prior to re-initiation of the study treatment, malignant disease will be radiologically re-staged to assess all known sites of the disease and to establish a new baseline for subsequent tumor measurements. Relevant safety laboratory results must be available and verified prior to re-initiating treatment. Subjects who re-initiate treatment will stay on study and will be treated and monitored according to the protocol and the Schedule of Assessments (Table 1).

The primary Phase I endpoints are:

- Occurrence and severity of treatment-emergent adverse events (TEAEs)  $\geq$  Grade 3 according to NCI-CTCAE v4.03
- DLTs to determine the RP2D

Safety endpoints include incidence of AEs and laboratory abnormalities assessed throughout the trial and evaluated using the National Cancer Institute Common Terminology Criteria for Adverse Events (NCI-CTCAE) v4.03, and vital signs.

#### 5.1.1.1.1 Modified Toxicity Probability Interval

Dose escalation/de-escalation rules will follow the mTPI method. Briefly, the mTPI method relies on a statistical probability algorithm to compute the posterior probability of 3 dosing intervals that reflect the relative difference between the toxicity rate of each dose level to the target probability rate ( $p_T = 0.3$ ), using all subjects treated in prior and current cohorts at the same dose level to determine whether future cohorts should involve dose re-escalation, no change in dose, or dose de-escalation. If the toxicity rate of the current dose is far smaller than  $p_T$ , the mTPI will recommend escalating the dose; if the toxicity rate is close to  $p_T$ , the mTPI will recommend continuing at the current dose; and if it is far greater than  $p_T$ , the mTPI will recommend de-escalation. Decision rules are based on calculating unit probability mass of 3 dosing intervals corresponding to under, proper, and overdosing in terms of toxicity. Specifically, the underdosing interval is defined as  $(0, p_T - e_1)$ , the overdosing interval as  $(p_T + e_2, 1)$  and the proper dosing interval as  $(p_T - e_1, p_T + e_2)$ , where  $e_1$  and  $e_2$  are small fractions. Based on the safety profile of avelumab,  $e_1$  is preselected as 0.05, and  $e_2$  is selected as 0.03. Therefore, the target interval for the DLT rate is (0.25, 0.33). The detailed dose-finding rules based on the mTPI are illustrated in [Table 3](#).

**Table 3 Detailed Dose Re-Escalation/De-Escalation Scheme**

		Number of Subjects Treated at Current Dose											
		1	2	3	4	5	6	7	8	9	10	11	12
Number of DLTs	0	NA	NA	E	E	E	E	E	E	E	E	E	E
	1	D	S	S	S	S	E	E	E	E	E	E	E
	2		DU	D	S	S	S	S	S	S	S	S	E
	3			DU	DU	D	D	S	S	S	S	S	S
	4				DU	DU	DU	D	D	S	S	S	S
	5					DU	DU	DU	DU	DU	D	S	S
	6						DU	DU	DU	DU	DU	DU	D
	7							DU	DU	DU	DU	DU	DU
	8								DU	DU	DU	DU	DU
	9									DU	DU	DU	DU
	10										DU	DU	DU
	11											DU	DU
	12												DU

E = Escalate to the next higher dose, or if current dose level is DL1, stay on DL1. Escalation to DL2 is allowed if exposure at DL1 is not adequate.

S = Stay at the current dose.

D = De-escalate to the next lower dose level.

DU = De-escalate to the next lower dose level; the current dose is unacceptably toxic.

Targeted DLT rate at MTD = 33%.

As an example, if the total number of subjects treated at DL1 is 3, then the following dosing rules will be applied:

- 0 or 1 DLT → remain at the same dose level (ie, DL1)
- 2 DLTs → de-escalate to DL -1 and allow for possible re-escalation to DL1
- ≥ 3 DLTs → de-escalate to DL -1, as DL1 is intolerable.

Rules for dose finding using the mTPI method will be the following:

- The target enrollment cohort size will be 3 to 6 subjects.
- The first cohort will initially comprise 3 subjects 1 to < 18 years of age at the time of first treatment dose at 10 mg/kg (DL1). Up to 3 additional subjects (0 to < 18 years of age) can be added if the first 3 subjects experience 0 or 1 DLT at DL1.
- After the first 3 subjects in the initial cohort are treated with DL1, PK data will be evaluated and drug exposure in these subjects versus adults will be analyzed to determine if exposure is adequate. Exposure data are required before any additional subjects are dosed.
- Inpatient dose escalation is not permitted.
- After each cohort, the number of DLTs will be assessed to determine the dose level for the next cohort using the mTPI design.
- DLTs will be reviewed by SMC members, and the decision to open each new cohort will be made by the SMC.
- The second and later cohorts will be enrolled when all subjects evaluable for DLT at the current dose cohort have been evaluated for at least 2 cycles (28 days), or when more than 1 subject in a cohort experiences a DLT, whichever comes first. The next cohort will receive the dose level as assigned if a dose modification is required.
- If DL1 is confirmed as safe, this dose will be selected as RP2D if it provides adequate exposure in children compared with adults.
- A decision can be made in a cohort defined by the SMC to test a dose level above 10 mg/kg (up to 20 mg/kg) if both of the following conditions are met:
  - Exposure achieved at 10 mg/kg does not reach therapeutic levels established in adults
  - 10 mg/kg was demonstrated to be safe.
- If a subject does not receive at least 2 infusions of avelumab within the DLT observation period (2 cycles = 28 days) for reasons other than study drug-related toxicity, another subject will be enrolled to replace that subject at the current dose level.
- Avelumab treatment will continue until:
  - Confirmed PD (see Section 5.5.1) or death
  - Unacceptable toxicity
  - Any criterion for withdrawal from the trial or trial treatment is fulfilled (see Section 5.5).
- Treatment can continue past the initial determination of confirmed disease progression per irRECIST (see Section 6.2).
- Phase I will be completed when at least 12 DLT-evaluable subjects have been treated at a dose level confirmed to be safe and similar exposure to that in adults is achieved.
- Additional subjects (up to 6 per cohort) can be enrolled at any dose level determined to be below the MTD to further assess variability of PK or safety by age.

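### The early-opening trigger after a second DLT is not limited to de-escalation, so in the first DL1 cohort a new cohort can start at the same dose while up to 2 children are still in their 28-day window

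*Protocol*

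**What the plan says.** The dose-finding rules under Table 3 in Protocol 5.1.1.1.1 let second and later cohorts enroll once every DLT-evaluable subject at the current dose has been followed for 28 days, "or when more than 1 subject in a cohort experiences a DLT, whichever comes first". No text confines the early branch to cases where the table calls for a lower dose. The first DL1 cohort starts with 3 children, and up to 3 more "can be added if the first 3 subjects experience 0 or 1 DLT at DL1".

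Table 3 gives these decisions:
- 2 DLTs: DU at n = 2, D at n = 3, Stay at n = 4, 5 and 6.
- 3 DLTs: DU at n = 4, D at n = 5 and 6.
- 4 DLTs: DU at n = 6.

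The columns are headed "Number of Subjects Treated at Current Dose", and the section describes the algorithm as "using all subjects treated in prior and current cohorts at the same dose level". Neither document says in words how a child with an open window enters the table.

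Two other provisions matter. Protocol 5.1.1.1 enrolls the next subjects at DL -1 whenever, at any point, the mTPI result calls for de-escalation. Under Protocol 2.3 the SMC "will decide by consensus on dose escalation, dose de-escalation, suspension of enrollment".

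**The concern.** The 28-day wait exists so that the table is read on complete information. The early trigger removes it at the moment toxicity has appeared. That makes sense if the table already orders a lower dose. It makes less sense at 2 DLTs among 4 to 6 children, where the table orders the same dose and one further DLT would reverse that. Children could then be started on a dose that the same table withdraws days later, in a population that reaches down to birth.

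**Working it through.** **Inputs.** From Protocol 5.1.1.1.1: target pT = 0.3, e1 = 0.05, e2 = 0.03 (target interval 0.25 to 0.33), cohort sizes 3 to 6, the 3 + 3 staging of the first cohort, and the trigger at 2 DLTs. Assumed: true DLT rates p of 10%, 20%, 30% and 40%; the first 3 windows closed before the 3 additions; same-day entry of those 3; table read at the second DLT.

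**Step 1: reproduce Table 3.** Posterior Beta(1 + x, 1 + n - x). Unit mass is posterior probability divided by interval length for (0, 0.25), (0.25, 0.33) and (0.33, 1). DU applies if P(rate > 0.30) > 0.95. The uniform prior and the 0.95 cut are not stated in the documents; with them, 88 of 88 printed decisions (the 2 NA cells aside) are reproduced.

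**Step 2: what the table says when the trigger fires in the 3 + 3 cohort.**

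| Path | Still pending | Pending counted | Pending left out | One more DLT | Two more |
|---|---|---|---|---|---|
| A: 1 DLT in first 3, then 1 among the added 3 | 2 | 2/6 = S | 2/4 = S | 3/6 = D | 4/6 = DU |
| B: 0 in first 3, then 2 among the added 3 | 1 | 2/6 = S | 2/5 = S | 3/6 = D | not possible |

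Both ways of counting give Stay, so relabelling the table does not close the gap.

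**Step 3: how often.** Let b(k) be the binomial probability of k DLTs in 3 children.
- Trigger fires at Stay: b(1) × [1 - b(0)] + b(0) × [b(2) + b(3)]
- Of these, final count D or DU: b(1) × [b(2) + b(3)] + b(0) × b(3)
- Of these, final count DU: b(1) × b(3)

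| p | b(0) | b(1) | b(2)+b(3) | b(3) | Trigger at Stay | Ends D or DU | Ends DU |
|---|---|---|---|---|---|---|---|
| 10% | 0.729 | 0.243 | 0.028 | 0.001 | 8.6% | 0.8% | 0.02% |
| 20% | 0.512 | 0.384 | 0.104 | 0.008 | 24.1% | 4.4% | 0.3% |
| 30% | 0.343 | 0.441 | 0.216 | 0.027 | 36.4% | 10.5% | 1.2% |
| 40% | 0.216 | 0.432 | 0.352 | 0.064 | 41.5% | 16.6% | 2.8% |

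Example at 30%: 0.441 × 0.216 + 0.343 × 0.027 = 0.0953 + 0.0093 = 0.105.

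**Step 4: sensitivity to timing.** With a constant hazard, entries 0 to 7 days apart and the table read 0 to 7 days after the trigger, simulation lowers the D-or-DU figures to at least about 0.4% / 2.4% / 5.5% / 8.8%. The review delay drives most of the drop, because some further DLTs are then seen before the decision.

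**Step 5: six children entered together at another dose level.** If pending children count as DLT-free, 2/6 = S with 4 pending, and the chance of finally reaching D or DU is P(at least 3 of 6) = 1.6% / 9.9% / 25.6% / 45.6%. If they are left out, the resolved data are 2/2 = DU and the same-dose problem disappears. These larger figures therefore depend entirely on the counting rule.

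**The case against.** Three stronger readings are tempting, and the documents do not support them.

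*That Table 3 treats pending children as DLT-free, so the cohort-of-6 figures apply.* The column heading and the description of the algorithm suggest this. But Protocol 8.4 defines the DLT Analysis Set as the subjects whose data drive dose escalation and requires all doses in the first 2 cycles or a stop for DLT. SAP 6 bases the SMC output on that set, and SAP 8.2 adds 28 days of follow-up. Together these point to leaving pending children out.

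*That nothing makes anyone look at the table again.* Protocol 5.1.1.1 applies the mTPI result at any point and to the next subjects, so a late DLT that changes the cell moves enrollment down then. The same rule covers 2/3 = D becoming 3/3 = DU.

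*That a whole further cohort of 3 to 6 is put on an unacceptably toxic dose.* Only children dosed before the next DLT are exposed, and most adverse outcomes end at D, which does not label the dose unacceptable. For 2 of 3 the protocol pairs D with the words "and allow for possible re-escalation to DL1". At true rates of 10% to 30% the dose is at or below the target interval, so Stay is not overdosing; only 40% lies above it.

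Further points count for the plan. The SMC decides on every cohort and may suspend enrollment. Protocol 5.1.1.1 speaks of setting the next dose when the first cohort is complete. The sentence after the trigger suggests that it was meant for dose changes. In adults, "there was no evidence of differences in the safety profile across all administered dose levels from 1 mg/kg to 20 mg/kg", so the low rates may be the relevant ones. SAP version 2.0 records that monotherapy evaluation ended after Phase I, which limits the effect of any change in this trial.

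All of that reduces the size of the point. It does not alter the trigger's wording: early opening is allowed on a Stay result, and in the 3 + 3 cohort Stay results under either count. The SMC Charter is not among the documents, so a rule for pending children can be neither assumed nor ruled out.

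**Conclusion.** The concern holds in a limited form. The written trigger permits a same-dose cohort to open with 1 or 2 children of the first DL1 cohort still in their DLT window. The chance that this happens and the table finally reads D or DU is about 0.8% / 4.4% / 10.5% / 16.6% at true rates of 10% / 20% / 30% / 40%; for DU it is about 0.02% / 0.3% / 1.2% / 2.8%. These are upper-end figures: they assume that the table is read at the second DLT and that the SMC does not hold enrollment, and slower review roughly halves them. They also assume that the first 3 windows have closed before the additions, which the protocol does not explicitly require. The priority is modest, but the change improves safety cheaply.

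**What to change.** In Protocol 5.1.1.1.1, carried into the SMC Charter:

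1. When more than 1 subject in a cohort has a DLT, dose no new subjects, including replacements, at the current or a higher level.
2. Open the lower level at once if Table 3 gives D or DU even with every pending subject counted as DLT-free (for example 2/3, 3/5, 3/6). That result cannot be reversed by the open windows.
3. Otherwise (2/4 to 2/6) wait until the pending 28-day windows close, then read the table.
4. At DL -1, where no lower level is defined, suspend enrollment pending SMC review.
5. As consistency edits, head Table 3 with DLT-evaluable subjects, with item 2 as the one stated exception, and say that the at-any-point rule in 5.1.1.1 includes late DLTs from pending subjects.

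The cost is a few sentences and a wait of at most 28 days after the last entry (mean 7 to 23 days in the simulated timings), with no extra subjects. At a true rate of 10%, the wait would apply to at most about 9% of 3 + 3 cohorts. Rapid de-escalation is kept where the table already supports it.
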